- b. The run-in start visit should generally be 1 week after the screening visit (with a recommended window of +/- 4 days). Subjects who at screening may require testing of pancreatic autoimmunity (ie, GAD-65 and/or IA antibodies) or who require a repeat of other screening procedures may have the duration of the screening period and/or run-in period increased by 1 to 2 weeks to allow sufficient time for the assessments to be obtained.
- c. Subjects who have a Week 12 HbA₁c of ≥7.0% and eGFR ≥60 mL/min/1.73m² will be re-randomized to either remain on double-blind canagliflozin 100 mg (or matching placebo) or to up-titrate to double-blind canagliflozin 300 mg (or matching placebo). See Section 9.1.4.3, Re-randomization.
- d. Early withdrawal visit evaluations will be performed in subjects who prematurely discontinue study drug (see Section 10.2, Study Drug Treatment Premature Discontinuation, Reinstitution, and Follow-up) and in subjects who withdraw consent from the study (either on their own and/or by their parents[s]/legal guardian[s]). See Section 10.3, Withdrawal from the Study). The early withdrawal visit evaluation should be performed as soon as possible after the last dose of study drug is taken.
- e. A telephone follow-up contact (or optional study visit, at the discretion of the investigator) will be conducted for all subjects approximately 30 days after the last dose of study drug to collect serious adverse events and adverse events of interest since the last visit unless the subject has died, has been lost to follow-up, or has withdrawn consent. If a telephone contact or study visit is not possible, follow-up information may be collected via email or other electronic means. This follow-up is not required in subjects who discontinue study drug prematurely and continue to attend all subsequent study visits. At this telephone contact, investigators should ask subjects about any foot problems and remind them about routine preventative foot care and early intervention for foot problems.
- f. The informed consent form for the parent(s)/legal guardian(s) (and the assent form for minor subjects, as described in Section 16.2.3, Informed Consent/Pediatric Assent) must be signed before any study procedure is performed.

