- x. Specific details about specimen collection, storage, packaging, and shipping will be provided in the laboratory manual. For FPG, fasting C-peptide, and lipids, subjects must be fasting for at least 8 hours before blood sample collection, except for the screening visit when non-fasting blood samples may be collected. A set of plasma, serum, and urine samples will be collected at each specified time point. The urine collections for routine urinalyses and exploratory specimens should be obtained from a spot urine specimen in the clinic.
- y. Hematology and serum chemistry are performed at the screening visit and should not be repeated at baseline, unless the screening visit was performed more than 4 weeks before the baseline visit. No fasting lipid panel will be collected at the Screening Visit; please ensure to collect fasting lipid panel at the Baseline visit/Day 1.
- z. Serum (β-human chorionic gonadotropin [β-hCG] pregnancy testing will be performed for all female subjects of childbearing potential at the screening visit. Additional urine (or serum) pregnancy tests may be conducted throughout the study in sufficient number, as determined by the investigator or required by local regulations, to establish the absence of pregnancy during the study. Serum pregnancy test must be performed and the result reviewed before randomization.
- aa. The urine sample for albumin/creatinine ratio should not be collected if the subject is menstruating, has exercised vigorously in the past 24 hours, or had a fever or an active infection within the past 2 days of the clinic visit.
- bb. Subjects will be given urine collection containers at each of the clinic visits preceding the first morning urine collection time points. The subject will provide a urine specimen from the first morning void on the morning of the clinic visit. If the subject does not provide the morning void collection on the day of the visit, the subject may bring a first morning void specimen to the investigational site during the subsequent week. For subjects who have atypical sleep patterns, the collection should be made at the end of the subject's usual sleep period. Study research staff is encouraged to contact the subject before this clinic visit as a reminder to the subject that he/she will need to provide a urine specimen at a particular visit (only 1 urine specimen is necessary at the indicated visit for the determination of albumin/creatinine ratio).

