- 6. Each subject (or their legally acceptable representative) must sign an informed consent form (ICF) indicating that he or she understands the purpose of and procedures required for the study and are willing to participate in the study. Assent is also required of children capable of understanding the nature of the study (approximately 7 years of age and older) as described in Section 16.2.3, Informed Consent/Pediatric Assent.
- 7. Before randomization, a female subject must be either:
  - a. Not of childbearing potential defined as:
    - premenarchal
    - permanently sterile (eg, bilateral tubal occlusion [which includes tubal ligation procedures as consistent with local regulations]), hysterectomy or bilateral salpingectomy, bilateral oophorectomy); or otherwise be incapable of pregnancy, or
  - b. Of childbearing potential and
    - heterosexually active *and* practicing a highly effective method of contraception (failure rate of <1% per year when used consistently and correctly) including combined (estrogen- and progestogen-containing) hormonal contraception associated with inhibition of ovulation: oral, intravaginal, and transdermal; progestogen-only hormone contraception associated with inhibition of ovulation: oral, injectable, or implantable; intrauterine device (IUD); intrauterine hormone-releasing system (IUS); vasectomized partner (provided that the partner is the sole sexual partner of the female subject of childbearing potential and the absence of sperm has been confirmed; if not, additional highly effective method of contraception should be used), and agrees to remain on a highly effective method

of contraception throughout the study and for at least 30 days after the last dose of study drug.

**Note:** Typical use failure rates may differ from those when used consistently and correctly. Use should be consistent with local regulations regarding the use of contraceptive methods for subjects participating in clinical studies.

• not heterosexually active (ie, female subject agrees to refrain from heterosexual intercourse during the entire period of risk associated with the study drug).

**Note**: Female subjects who are not heterosexually active at screening must agree to utilize a highly effective method of contraception if they become heterosexually active during their participation in the study.

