- 8. Female subjects of childbearing potential must have a negative highly sensitive serum  $\beta$ -human chorionic gonadotropin ( $\beta$ -hCG) pregnancy test at the screening visit.
- 9. Adequate compliance with placebo single-blind run-in procedures, including ≥80% compliance (by tablet count) with single-blind placebo medication.

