## Laboratory

8. Persistent elevation in capillary blood ketones ≥0.6 mmol/L in the absence of concomitant illness or other identified precipitating factor during the screening period. Persistent elevation is defined as capillary blood ketone values ≥0.6 mmol/L obtained on ≥2 consecutive days.

**Note:** Subjects with capillary ketone levels  $\geq 0.6$  mmol/L in the presence of precipitating factors (eg, acute illness, non-compliance with insulin treatment) may have the screening or run-in period extended by up to 2 weeks if it is the investigator's opinion that precipitating factor/concomitant illness will be resolved and the subject will no longer meet the exclusion criterion. If, following resolution of the precipitating factor(s), the repeat assessment of capillary blood ketones shows values  $\geq 0.6$  mmol/L, the subject must be excluded.

**Note:** To avoid the confounding effect of overnight fasting on ketogenesis, for the pre-specified ketone assessment procedures, the blood ketone measurements should be obtained in a non-fasting state. If non-symptomatic ketone elevations are found in the fasting state, subjects should be instructed to repeat the ketone measurement after breakfast.

9. eGFR is <60 mL/min/1.73m^2 as assessed by Schwartz formula (see Attachment 7, Clinical Laboratory Tests).

**Note**: A one-time repeat measurement is allowed, at the discretion of the investigator, if the value for eGFR is not consistent with prior values.

10. Alanine aminotransferase level >5.0 times the upper limit of normal (ULN) or total bilirubin >1.5 times the ULN at screening (for elevations in bilirubin: if, in the opinion of the investigator and agreed upon by the sponsor's medical officer, the elevation in bilirubin is consistent with Gilbert's disease, the subject may participate).

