#### 9.1.1.1. Visit Schedules and Visit Windows

A screening visit should occur approximately 1 week before the single-blind placebo run-in visit (Week -2). The single-blind placebo run-in period should be 2 weeks in length, with a recommended visit window of ±4 days.

**Note**: Subjects who at screening may require testing of pancreatic autoimmunity (ie, GAD-65 and/or islet cell antigen [IA] antibodies) or who require a repeat of other screening procedures may have the duration of the screening period and/or run-in period increased by 1 to 2 weeks to allow sufficient time for the assessments to be obtained.

Post-randomization (from Day 1) scheduled study visits should generally occur within a recommended 7-day window (ie,  $\pm 7$  days) around the protocol-specified visit schedule (as provided in the Time and Events Schedule). All visits will be scheduled based on the date of randomization (Day 1). There may be exceptional cases where it is possible, with concurrence of the sponsor's medical monitor, that certain on-site study visits may be replaced by telemedicine visits (a remote visit that is done by a video or phone call.).

A telephone follow-up contact (or optional study visit, at the discretion of the investigator) will be conducted for all subjects approximately 30 days after the last dose of study drug. If a telephone contact or study visit is not possible, follow-up information may be collected via email or other electronic means.

In the event that it is impossible for a subject to make a scheduled clinic visit, telephone contacts may be conducted at the time of the missed visit, but a clinic visit should be scheduled as soon as possible thereafter. If a telephone contact or study visit is not possible, follow-up information may be collected via email or any other appropriate means. Details regarding discussions via telephone, email, or other such contacts must be properly documented in source records, including responses by the subject (or parent/guardian).

For study visits that are unable to be held within the protocol-recommended visit windows, the visit should be conducted as close as possible to the protocol-specified study visit timing. All subsequent visits should be scheduled based on the date of randomization, not the date of the rescheduled visit.

For subjects who prematurely discontinue study drug, but don't withdraw consent, study sites will be required to follow-up on subsequent scheduled visits, and to make a final contact

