**Note**: If the subject does not meet the eligibility criteria related to compliance with study procedures during the run-in period due to unforeseeable circumstances (eg, breakage or loss of the meter, or intercurrent illness that prevented the subject to be compliant with single-blind study drug, etc), at the discretion of the investigator and with concurrence of the sponsor's medical monitor, the duration of the run-in period may be extended to repeat the procedures and allow assessment of eligibility. In such cases, subjects may receive additional single-blind study drug.

Potential subjects who do not meet all entry criteria must be excluded from the study.

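### The screening serum test is the only pregnancy test required before first dose, and it has no maximum age, while hematology and chemistry from the same visit are repeated after 4 weeks

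*Protocol*

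**What the plan says.** Inclusion criterion 8 (Protocol 4.1) sets the pre-dose requirement: "Female subjects of childbearing potential must have a negative highly sensitive serum" pregnancy test, done at the screening visit. In the Time and Events Schedule the serum test is marked at screening only, and the urine test at Week 26 and at Week 52/EOT/early withdrawal. Sections 9.1.1.3 and 9.8 and Attachment 7 require no other test before dosing, and Table 3 in 9.1.1.6 budgets one serum β-hCG sample per subject. Footnote z adds: "Serum pregnancy test must be performed and the result reviewed before randomization". Any further tests depend on the investigator or on local regulation.

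Footnote y deals with old results for other tests. Hematology and serum chemistry are not to be repeated at baseline "unless the screening visit was performed more than 4 weeks before the baseline visit".

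Several provisions set or lengthen the time between screening and Day 1:

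- Footnote b puts the run-in start about 1 week after screening, give or take 4 days.
- Section 9.1.1.1 says: "The single-blind placebo run-in period should be 2 weeks in length, with a recommended visit window of ±4 days".
- Footnote b also says that subjects needing antibody testing or repeat screening procedures "may have the duration of the screening period and/or run-in period increased by 1 to 2 weeks".
- The note to exclusion 8 says that subjects with raised ketones and a precipitating factor "may have the screening or run-in period extended by up to 2 weeks".
- The note in 9.1.3 covers run-in compliance problems with an unforeseeable cause: "the duration of the run-in period may be extended to repeat the procedures and allow assessment of eligibility". It needs the medical monitor's agreement but gives no maximum.

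**The concern.** Pregnancy is exclusion 20, and it can arise between screening and Day 1. The closing paragraph of 4.2 says that a subject whose status changes after screening and who then meets an exclusion should not be randomized. Without a test, an early pregnancy with no symptoms can pass that review.

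Two things would follow. A subject would be randomized although ineligible, and a fetus would be exposed to study drug. If the pregnancy were missed on Day 1, no scheduled test would show it before Week 26 unless the subject withdrew early. Adverse event review at Weeks 3, 6, 12 and 20 might pick it up.

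The protocol treats such exposure as serious elsewhere. Study drug stops on a positive urine test and is permanently discontinued on serum confirmation (9.8, 10.2.1). Pregnancy is an adverse event of interest (Section 12), and initial reports are due within 24 hours (12.2.3).

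**Working it through.** **Age of the screening test at first dose.** Inputs: 7 days from screening to run-in and 14 days of run-in, each with a +4-day window (footnote b; 9.1.1.1), and an extension of up to 2 weeks (footnote b; exclusion 8 note).

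- Planned: 7 + 14 = 21 days, which agrees with the schedule's Week -3 screening visit.
- Both windows at their upper end: (7 + 4) + (14 + 4) = 29 days.
- One period extended by 2 weeks: 21 + 14 = 35 days (43 with both windows).
- Both periods extended by 2 weeks: 21 + 28 = 49 days (57 with both windows). This is a conditional upper case, because footnote b can also be read as 1 to 2 weeks in total.
- Run-in compliance extension (9.1.3): no maximum stated, so no upper limit can be calculated.

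The footnote y threshold is 4 × 7 = 28 days. Every case except the planned one exceeds it.

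**Time from the screening test to the next scheduled test.** This is the gap in weeks plus 26: 3 + 26 = 29, 5 + 26 = 31 and 7 + 26 = 33 weeks.

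**Female subjects.** Section 3.1 has a goal of 30% to less than 65% female in each age group. With 146 subjects, 0.30 × 146 = 43.8 (about 44) and 0.65 × 146 = 94.9 (at most 94). Premenarchal and sterile subjects would be subtracted.

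**Expected pregnancies before dosing, upper bound.** The formula is subjects × years waited × yearly rate. If all 94 waited 7 weeks, exposure is 94 × 7/52 = 12.65 person-years.

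- At 1% per year (inclusion 7 cites below 1% with correct use): 12.65 × 0.01 = 0.13.
- At an assumed 5%: 12.65 × 0.05 = 0.63.
- At an assumed 10%: 12.65 × 0.10 = 1.27.

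**A more moderate case.** Assume that 10% to 30% of the 94 have a 35-day gap. Exposure is 9.4 × 5/52 = 0.90 to 28.2 × 5/52 = 2.71 person-years. That gives about 0.01 to 0.03 pregnancies at 1%, and about 0.05 (0.90 × 0.05) to 0.27 (2.71 × 0.10) at 5% to 10%.

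**Existing safeguards.**

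- Contraception or abstinence (inclusion 7) lowers the risk, but the same criterion notes: "Typical use failure rates may differ from those when used consistently and correctly".
- Eligibility review through Day 1 (footnote g; end of 4.2) names no test.
- Additional tests under footnote z are discretionary unless local regulation requires them.
- Rescreening (4.4) typically repeats all screening tests, but only after a recorded screen failure. The COVID-19 appendix sends subjects who miss the run-in window down that route. Neither applies to a subject within a permitted extension.

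None of these makes a test compulsory between screening and first dose.

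**The case against.** The strongest reply is that this is a consistent design choice. The pregnancy-testing sections do not contradict each other, and the argument for 28 days is by analogy with footnote y, which concerns blood tests. Section 4.2 also places an active duty on the investigator to establish that nothing has changed clinically since screening, and footnote z gives the means to test. On this view, a site that relies on an old result without making that determination has not met its duty. The duty is real, but a site can review history and symptoms in good faith, order no test, and still have done what the text requires.

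The numbers are also open to challenge. The 49-day figure depends on one reading of footnote b, and the 29-day figure passes the threshold by a single day. The upper bound puts every female subject at the longest gap, and the 5% and 10% rates are not in the documents. Nor is 94 a firm cap, since it comes from an enrollment goal and the SAP (1.2, 1.5) gives 30% to 75% female. All of this stands, and it limits the size of the problem. It does not remove the 35-day case, which needs only one permitted extension.

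Finally, the remedy is partial. Gaps of 4 weeks or less stay untested, and so do the 26 weeks on drug, which amount to 94 × 26/52 = 47 person-years against at most 12.65 before dosing. That is correct. On-treatment testing frequency is a separate question. The point here is narrower: eligibility at first dose should not rest on a result older than the protocol accepts for hematology and chemistry.

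**Conclusion.** The gap is real. The protocol requires one pregnancy test before dosing and sets no maximum age for it, and a compliant site can exceed the 4-week limit applied to hematology and chemistry from the same visit: 29 days on windows alone, 35 with one extension, and 49 if footnote b allows both periods to be extended.

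The expected number of cases is small. The upper bound is 0.13 pregnancies at 1% per year and 0.6 to 1.3 at assumed rates of 5% to 10%. The true figure should be lower, because most gaps should be near 3 weeks and some female subjects are not of childbearing potential. Sample size, power and type 1 error are not affected. The change is worth making because it closes a preventable route to fetal exposure at very little cost, but it is a recommended safety improvement and not a flaw that undermines the trial.

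**What to change.** Add one sentence to footnote z, with a cross-reference in inclusion criterion 8: if the screening pregnancy test was done more than 4 weeks before the baseline visit, repeat a urine or serum test and review a negative result before the first dose on Day 1. This uses the footnote y threshold.

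A urine test would suffice, with a positive result confirmed by serum as 9.8 already provides. Day 1 urinalysis is taken from a spot specimen in the clinic, so no additional urine collection is needed, and no blood draw unless a positive result has to be confirmed. The cost is one simple test, only for female subjects of childbearing potential whose screening was more than 4 weeks before Day 1. Subjects on the planned 3-week timetable need nothing extra.

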## **ABBREVIATIONS**

ACR albumin/creatinine ratio ADA American Diabetes Association

ADR adverse drug reaction
AHA antihyperglycemic agent
AUC area under the curve
BMD bone mineral density
BMI body mass index

CANVAS Canagliflozin Cardiovascular Assessment Study

CI confidence interval

CRF case report form (paper or electronic as appropriate for this study)

CSR clinical study report
CV cardiovascular
CTx carboxy-telopeptide
DKA diabetic ketoacidosis

DXA dual energy X-ray absorptiometry eCRF electronic case report form eDC electronic data capture

eGFR estimated glomerular filtration rate EMA European Medicines Agency

EOT end-of-treatment EU European Union FAS full analysis set

FDA Food and Drug Administration

FPG fasting plasma glucose
GAD glutamic acid decarboxylase
GCP Good Clinical Practice
HbA1c glycated hemoglobin

hCG human chorionic gonadotropin HDL-C high-density lipoprotein-cholesterol

IA2 islet cell antigen 2
IB Investigator's Brochure
ICF informed consent form

ICH International Conference on Harmonisation

ID identification

IDMC Independent Data Monitoring Committee

IEC Independent Ethics Committee

IR immediate release

IRB Institutional Review Board IWRS interactive web response system

LADA latent autoimmune diabetes of adulthood

LC-MS/MS liquid chromatography/mass spectrometry/mass spectrometry

LCT Leydig cell tumors

LDL low-density lipoprotein-cholesterol

LH Luteinizing hormone

LOCF last-observation-carried-forward

MedDRA Medical Dictionary for Regulatory Activities

MMRM mixed model for repeated measures
MODY Maturity-Onset Diabetes of the Young
MSRC Medical Safety Review Committee

MTD maximum tolerated dose PD pharmacodynamics

PDC Pediatric Diabetes Consortium

PG plasma glucose PI package insert PK pharmacokinetic PP per protocol

PPG post-prandial plasma glucose
PQC product quality complaint
PTH parathyroid hormone
RTG renal threshold for glucose
SAE serious adverse event
SAP Statistical Analysis Plan
SD standard deviation

SGLT2 sodium-glucose co-transporter 2

SU sulphonylurea

SMBG self-monitoring of blood glucose

SUSAR suspected unexpected serious adverse reaction

T1DM type 1 diabetes mellitus
T2DM type 2 diabetes mellitus
UGE urinary glucose excretion
UGT UDP-glucuronosyltransferases

ULN upper limit of normal

US United States

UTI urinary tract infection XR extended release

Status: Approved, Date: 14 August 2020

## **DEFINITIONS OF TERMS**

Cmax maximum plasma drug concentration

tmax time to reach the maximum observed plasma concentration

t1/2 elimination half-life (to be used in one or noncompartmental model)

## 1. INTRODUCTION

Canagliflozin (JNJ-28431754) is an inhibitor of the sodium-glucose co-transporter 2 (SGLT2) that has been developed as an oral antihyperglycemic agent (AHA) for the treatment of adults with type 2 diabetes mellitus (T2DM). It has been approved by several Health Authorities, including the United States (US) Food and Drug Administration (FDA) and the European Medicines Agency (EMA). Canagliflozin is used as an adjunct to diet and exercise to improve glycemic control in adults with T2DM; to reduce the risk of major adverse cardiovascular (CV) events in adults with T2DM and established CV disease; and to reduce the risk of end-stage kidney disease, doubling of serum creatinine, CV death, and hospitalization for heart failure in adults with T2DM and diabetic nephropathy with albuminuria. (Not all indications are approved in all markets.)

Type 2 diabetes mellitus is a chronic, progressive disorder that occurs across a broad age range, is rarely seen in children <10 years of age and occurs with rising incidence as age increases. Once diet and exercise are no longer sufficient, children, adolescents, and adults with T2DM may initially have adequate glycemic control with a single oral agent, usually metformin. Over time, however, maintaining good glycemic control requires the use of combinations of oral agents, then insulin in combination with oral agents, and finally the implementation of a multi-injection per day insulin regimen. Recent clinical treatment guidelines published by the American Academy of Pediatrics state that all youth with newly diagnosed T2DM should be treated immediately with insulin, if pre-specified criteria are met. In all other cases, treatment with metformin should be initiated (Copeland 2013). Thus, treatment-naïve patients, managed only with diet and exercise, are very uncommon. Currently, in addition to insulin, the only FDA and EU approved oral agent in children and adolescents ≥10 years of age with T2DM is metformin. Therefore, there is an unmet need for additional options to treat children and adolescents ≥10 years of age with T2DM.

The present study will examine the efficacy and safety of canagliflozin in children and adolescents ≥10 and <18 years of age. This is a 52-week randomized, double-blind, placebo-controlled, parallel-group study, consisting of a 26-week core double-blind treatment period followed by a 26-week extension double-blind treatment period. Eligible subjects will be either on diet and exercise alone, on diet and exercise and a stable dose of metformin monotherapy, on diet and exercise and a stable insulin monotherapy regimen, or on diet and exercise and a stable combination therapy with metformin and insulin. The results of this study plus the available extensive data in the adult population with T2DM as well as model-based analyses on exposure-response pharmacokinetics/pharmacodynamics (PK/PD) in adults and children/ adolescents, is expected to provide sufficient information to assess the benefit/risk ratio of canagliflozin in pediatric subjects with T2DM.

The term "sponsor" used throughout this document refers to the entities listed in the Contact Information page(s), which will be provided as a separate document.

